14. Ophthalmic exam: best corrected visual acuity, pupil exam, color vision assessment, Ishihara color plates (or equivalent) or related red desaturation, intraocular pressure, and slit lamp exam. If significant abnormalities are noted compared to previous visits, including a loss of 2 lines or more of vision, development of pupil abnormalities including APD, rise in intraocular pressure, development of corneal infiltrates or other abnormalities not here specified but of concern to the ophthalmologist, further investigations of visual function will be conducted according to the ophthalmologist decision.
15. Vital signs (heart rate, blood pressure, respiratory rate, temperature) will be measured at all clinic visits. Vital signs will be measured pre- and post-infusion on Day 1 and Week 3, and pre-dose on all other infusion days. Additional vital signs will be monitored if infusion-associated AEs occur (see [Section 9.5.4.3](#) for details).
16. Non-diabetic subjects should be fasting at Weeks 1 and 4 only. Diabetic subjects should be fasting at each visit blood glucose is evaluated.
17. ALT/AST must be  $\leq 3$  x the upper limit of normal (ULN) and serum creatinine must be  $< 1.5$  x the ULN (according to age) at the most recent clinic visit to be eligible for enrollment.
18. Subjects must be euthyroid with the baseline disease under control or have mild hypo- or hyperthyroidism (defined as free thyroxine [FT4] and free triiodothyronine [FT3] levels < 50% above or below the normal limits) at the most recent clinic visit. Every effort should be made to correct the mild hypo- or hyperthyroidism promptly and to maintain the euthyroid state for the full duration of the clinical trial.
19. HbA1c must be < 9.0% at the most recent clinic visit. If the HbA1c is elevated and considered clinically significant at any time point after Baseline, it will be repeated approximately every 45 days until it returns to normal or the baseline value.
20. If a sample is positive in the ADA test, after confirmatory and reactive titer testing, the sample will then be tested for NAb. If the subject tests positive for NAb, he/she will be followed until levels either revert to Baseline or the subject's value decreases or remains stable. Any subject with a positive NAb test at Week 48 (or PW) during the Follow-Up Period will continue to be followed until the subject's value decreases or remains stable.

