#### Hyperglycemia

In preclinical studies, there was no *in vitro* cross-reactivity of teprotumumab with the insulin receptor. During TED01RV, among non-diabetic subjects, hyperglycemia occurred at comparable rates in both treatment groups and was uniformly Grade 1 and intermittent. Among diabetic subjects, Grade 2 or 3 hyperglycemia occurred in some teprotumumab-treated subjects; this was well-controlled after diabetes medication adjustment. Glycemic control, as assessed by HbA1c, was at baseline levels following the treatment phase for all subjects in the teprotumumab group.

Subjects with known controlled diabetes mellitus are allowed to participate in studies with teprotumumab. HbA1c levels should be monitored regularly in these subjects. Investigators are strongly encouraged to adjust their subjects' diabetes management to maintain subjects' HbA1c levels at  $\leq 7\%$ . In the event a subject's HbA1c level rises to  $> 7\%$  while in the study, the Investigator must determine the risk versus benefit for each subject to remain in the study.

Fasting glucose levels (after at least an 8-hour fast) should be tested at Baseline. Hyperglycemia should be promptly investigated and managed. Subjects with recurrent hyperglycemia, defined as a fasting glucose level of moderate intensity (glucose  $> 160 - 250$  mg/dL), will require evaluation for diabetes mellitus (e.g., fasting glucose, glucose tolerance, and HbA1c tests) and appropriate medical management at the discretion of the Investigator.

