Increase in blood glucose is a known AE observed in previous clinical trials with teprotumumab and other IGF-1R antagonists and is known to respond to treatment. Since a referral for treatment of hyperglycemia may take some time, if the Investigator considers it appropriate to continue the subject in the study, the next scheduled infusion visit may be skipped to allow modified anti-diabetic treatment to show its activity and hyperglycemia to return to mild/moderate level before dosing. The subject would then be dosed at the next scheduled visit (i.e., 6 weeks after the previous infusion). Fasting blood glucose levels must return to mild/moderate severity before the next scheduled infusion. The above process of withholding a scheduled infusion will be permitted only twice during the study.

Any changes to the scheduled dosing interval (q3W) or adjustments in the infusion rate should be reported to the Sponsor/CRO.

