6.2.3. Study Baseline and HZN-001 Baseline

The following two definitions of baseline will be utilized for analysis purposes:

- **Study Baseline** will be defined as the last measurement taken prior to first dose in HZNP-TEP-302 (considering unscheduled visits when available). If a Study Baseline value is not obtained in the HZNP-TEP-302 study prior to dosing, the last value measured in HZNP-TEP-301 will be used. Study Baseline comparisons will be provided for all applicable endpoints.
- **HZN-001 Baseline** will be defined as the last measurement taken prior to first dose of HZN-001 whether it occurred in HZNP-TEP-301 or HZNP-TEP-302 (considering unscheduled visits when available). HZN-001 Baseline comparisons will be provided for select assessments of safety, i.e. laboratory assessments, vital signs, ECGs, physical examinations, and ophthalmic examinations.

Change from (Study or HZN-001) Baseline will be defined as the measurement at each time point minus the relevant Baseline value.

The primary objective will be assessed using the Study Baseline.

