10.8. CLINICAL LABORATORY SAFETY EVALUATIONS

With the exception of urine pregnancy tests, a central study laboratory will be used for all protocol-specified clinical laboratory parameters. [Table 3](#) provides the schedule of collection.

Table 3 Schedule of Clinical Laboratory Safety Tests, Including Thyroid Panel and Hyperglycemia Monitoring

Analysis Panel	Treatment Period											Follow-Up Period		
	BL ¹	W1	W3	W4 M1	W6	W9	W12 M3	W15	W18	W21	W24 M6	W28 M7	W36 M9	W48 M12
Chemistry (excl. glucose)	X ²		X		X	X	X		X		X		X	X
Thyroid (FT3, FT4, TSH) ³	X		X		X	X	X		X		X		X	X
Hematology	X	X	X	X	X	X	X	X	X	X	X		X	X
Glucose ⁴	X	X	X	X	X	X	X	X	X	X	X		X	X
HbA1C	X ⁵						X				X		X	X
Urinalysis	X		X		X	X	X		X		X		X	X
Urine pregnancy ⁶	X		X		X	X	X	X	X	X	X	X	X	X

BL=Baseline; FT3=free triiodothyronine; FT4=free thyroxine; HbA1C=glycated hemoglobin A1C; M=Month; SCR=Screening; TSH=thyroid stimulating hormone; W=Week.

1. If Day 1 (Baseline) of the extension study occurs on the same day as the final visit of HZNP-TEP-301, assessments do not need to be repeated, and the final assessments from the lead-in study will serve as the Baseline assessments for the extension study.
2. ALT /AST must be ≤ 3 x the ULN and serum creatinine must be < 1.5 x the ULN (according to age) at most recent clinic visit for enrollment.
3. Subjects must be euthyroid with the baseline disease under control or have mild hypo- or hyperthyroidism (defined as FT4 and FT3 levels < 50% above or below the normal limits) at the most recent clinic visit. Every effort should be made to correct the mild hypo- or hyperthyroidism promptly and to maintain the euthyroid state for the full duration of the clinical trial.
4. Non-diabetic subjects will fast at Weeks 1 and 4 only. Diabetic subjects will fast for each blood glucose evaluation. NOTE: Subjects with severe hyperglycemia that does not abate to mild or moderate intensity with anti-diabetic treatment (dose may be skipped up to 2 times prior to permanently discontinuing study drug, see Section 9.4.6.3.2 for details) will be permanently discontinued from study drug.
5. HbA1C must be < 9.0% at most recent clinic visit for enrollment. If the HbA1C is elevated and considered clinically significant at any time point after Baseline, it will be repeated approximately every 45 days until it returns to normal or baseline value.

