6. Perform for female subjects of childbearing potential (including those with an onset of menopause <2 years prior to Screening of HZNP-TEP-301, non-therapy-induced amenorrhea for <12 months prior to Screening of HZNP-TEP-301, or not surgically sterile [absence of ovaries and/or uterus]).

Laboratory results collected in conventional units will be converted to International System of Units (SI) for all summaries and listings. Clinical laboratory test results (hematology, chemistry, thyroid panels, and urinalysis), their changes from Study Baseline, and their changes from HZN-001 Baseline will be summarized by visit and treatment received in HZNP-TEP-301 using descriptive statistics. If a continuous laboratory value is reported as either below or above the limits of quantification, the qualifiers will be dropped and the numeric value used in the analysis (e.g., “< 3” will be summarized as “3” and “> 200” will be summarized as “200”). For hematology, chemistry and thyroid panel, results will be categorized as low, normal, or high based on their normal ranges. For urinalysis tests, results will be classified as normal or abnormal. Results out of range will be identified as such on subject listings. Shift tables for hematology and chemistry panels using categories of low, normal, and high, comparing laboratory test results from

Study Baseline and HZN-001 Baseline to each visit will be presented overall and by treatment received in HZNP-TEP-301 with percentages based on subjects with a non-missing value at Baseline and post-baseline visit. Shift tables for urinalysis results using categories of normal and abnormal, comparing laboratory test results from Study Baseline and HZN-001 Baseline to each visit will be presented overall and by treatment received in HZNP-TEP-301 with percentages based on subjects with a non-missing value at Baseline and post-baseline visit. Additionally, a shift table for glucose by Common Terminology Criteria for Adverse Events (CTCAE) grade and visit will be presented overall and by treatment received in HZNP-TEP-301. Summaries will be provided separately for hyperglycemia and hypoglycemia.

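### Glucose tables compare fasting Week 1 and Week 4 samples with a non-fasting Baseline in non-diabetic subjects, and pool them with always-fasting diabetic subjects

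*SAP*

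**What the plan says.** SAP Table 3 schedules glucose at Baseline and at Weeks 1, 3, 4, 6, 9, 12, 15, 18, 21, 24, 36 and 48. Its note 4 reads: "Non-diabetic subjects will fast at Weeks 1 and 4 only. Diabetic subjects will fast for each blood glucose evaluation". Protocol Table 9.4 note 4 has the same rule, as does note 16 to the Protocol 2.1 schedule: "Non-diabetic subjects should be fasting at Weeks 1 and 4 only. Diabetic subjects should be fasting at each visit blood glucose is evaluated".

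The hyperglycemia text in Protocol 7.1.3.4.5.5.1 differs for Day 1: "Fasting glucose levels (after at least an 8-hour fast) should be tested at Baseline". It does not limit this to diabetic subjects.

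SAP 6.2.3 gives Study Baseline as "defined as the last measurement taken prior to first dose in HZNP-TEP-302", with no condition on fasting. For laboratory tests, SAP 10.8 summarizes results and changes from Study Baseline, and "their changes from HZN-001 Baseline will be summarized by visit and treatment received in HZNP-TEP-301 using descriptive statistics". It then adds for glucose that "a shift table for glucose by Common Terminology Criteria for Adverse Events (CTCAE) grade and visit will be presented overall" and by lead-in treatment. The table index has one such table for each of the two baselines.

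The protocol's clinical rules lean on fasting values. Recurrent hyperglycemia is "defined as a fasting glucose level of moderate intensity", with a range of above 160 to 250 mg/dL. After a skipped dose, "Fasting blood glucose levels must return to mild/moderate severity before the next scheduled infusion".

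**The concern.** A change or grade shift from Baseline is interpretable when both samples were taken in the same state. Here the state changes by design for one part of the population and not for the other, and no analysis rule takes account of it. The two affected visits under the schedule notes, Weeks 1 and 4, are the safety visits one week after each of the first two infusions.

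Hyperglycemia is an adverse event of special interest. In the earlier trial in this disease, the protocol describes it as the one event clearly attributable to the drug. A display that pushes early glucose changes downward therefore errs in the less cautious direction. Pooling adds a second difficulty: the two lead-in treatment columns can differ because their shares of diabetic subjects differ.

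**Working it through.** **1. Count the visits.** From SAP Table 3 there are 12 post-baseline glucose visits (none at Week 28). Subjects who relapsed in the lead-in study stop at Week 24 and have 10.

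| Subject and rule | Baseline | Weeks 1, 4 | Other visits | Mismatched with Baseline |
|---|---|---|---|---|
| Non-diabetic, schedule notes | not fasting | fasting | not fasting | 2 of 12 (relapse: 2 of 10) |
| Non-diabetic, Day 1 fasting | fasting | fasting | not fasting | 10 of 12 (relapse: 8 of 10) |
| Diabetic | fasting | fasting | fasting | 0 |

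**2. Find the direction.** Let F be a non-diabetic subject's fasting glucose before treatment, r the true rise, and d the excess of a non-fasting over a fasting value.

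- Schedule notes, Weeks 1 and 4: (F + r) − (F + d) = r − d.
- Day 1 fasting, other visits: (F + d + r) − F = r + d.

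The documents give no value for d. That d is positive is an assumption. For illustration only, take r = 10 mg/dL:

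| Assumed d (mg/dL) | r − d | r + d |
|---|---|---|
| 0 | 10 | 10 |
| 10 | 0 | 20 |
| 20 | −10 | 30 |
| 30 | −20 | 40 |

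**3. Add the pooling.** With diabetic share p and the same r in both groups, the pooled mean change at Weeks 1 and 4 under the schedule notes is r − (1 − p)d. Assume r = 10 and d = 20. For p = 10% this is 10 − 0.9 × 20 = −8; for p = 20% it is 10 − 0.8 × 20 = −6. Two columns with the same true rise would then differ by 2 mg/dL through case mix alone. The diabetic share is not in the documents.

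**4. Grade shifts.** These move in the same direction as the mean change. Percentages would need the glucose distribution, the variability after meals, the normal limit and the CTCAE cut-offs. The documents supply none of these as inputs for the graded table, so no percentage is given.

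**5. Look for a rule that prevents this.** The SAP mentions fasting only in schedule footnotes. Diabetic status is not among the SAP 6.6 subgroups, and those subgroup summaries cover efficacy and treatment-emergent adverse events, not laboratory data. The titles of Tables 14.3.4.1.2.3.1 and 14.3.4.1.2.3.2 name neither fasting state nor diabetic status. The mock-ups are in a separate file that was not available.

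**6. Limits of the reading.**
- The graded glucose shift is explicit in SAP 10.8. That glucose also sits in the chemistry change table is an inference: the protocol's visit lists place glucose within chemistry and the glucose shift tables carry chemistry numbers, but Table 3 lists chemistry without glucose.
- A same-day final lead-in visit may supply Baseline. For subjects given teprotumumab in the lead-in study, the HZN-001 Baseline comes from that study. Its fasting rule is not in these documents.

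**The case against.** The strongest reply is that the affected area is small. Three schedule notes agree that non-diabetic subjects fast at Weeks 1 and 4 only. The contrary text is a single recommendation in the protocol's introduction. On the main reading, 10 of 12 visits are matched within subject, and because the tables are by visit, Weeks 1 and 4 stand in their own rows. This stands and sets the scope, although nothing in the SAP tells the reader to treat those rows differently.

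A reader might infer that the plan hides hyperglycemia. The documents do not support that. On the main reading a sustained rise still appears at Week 3 and from Week 6 onward. HbA1c, which SAP 4.5 counts within chemistry, is collected at Baseline and Weeks 12, 24, 36 and 48. Hyperglycemia is also summarized as an adverse event of special interest through a standardized MedDRA query (SAP 10.3.1), and laboratory values are listed by subject. HbA1c cannot stand in for Weeks 1 and 4, because it is not scheduled between Baseline and Week 12.

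A reader might also infer from the protocol's fasting definitions that only fasting samples should be graded. That goes too far. Protocol 9.3.3 gives blood glucose above 250 mg/dL as its example of severe drug-related hyperglycemia, without requiring fasting. On the main reading, grading fasting samples only would leave non-diabetic subjects with grades at Weeks 1 and 4 alone, no matching Baseline, and high values at other visits ungraded.

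**Conclusion.** The point holds as a minor one. Following the SAP's own schedule rule, the graded glucose shift understates any rise in non-diabetic subjects at 2 of 12 post-baseline visits; so does the change table, if glucose is in it. At the other 10 visits the tables pool unlike samples across subjects. If Day 1 is in fact fasting, the mismatch moves to those 10 visits and reverses direction. The conflict between the protocol's hyperglycemia text and the schedule notes is real, but the two readings do not carry equal weight.

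Only the direction can be claimed, on the assumption that non-fasting glucose runs higher. The size cannot be derived from the documents, and the figures in mg/dL above only illustrate the algebra. The study is descriptive, and neither its primary endpoint nor any test is affected.

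**What to change.** Amend SAP 10.8 as follows:

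1. Present the glucose change and CTCAE shift tables by diabetic status, taken from medical history (SAP 7.3). If fewer than 5 subjects are diabetic, list their values instead.
2. Label the fasting state at each visit, from the sample record if it was collected and otherwise from the schedule rule, and say which was used.
3. State whether Day 1 is fasting for non-diabetic subjects. Where Baseline and visit differ in fasting state, show observed values and grades but no change or shift from Baseline.
4. Keep grading all samples, with fasting and non-fasting values in separately labelled rows, and give the CTCAE version and glucose cut-offs.

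The cost is SAP wording and a re-split of planned tables, with no new data collection. The downside is that non-diabetic subjects lose the change from Baseline at Weeks 1 and 4 or, if Day 1 is fasting, at the other visits. If fasting was not recorded, classification by schedule is approximate and the table should say so.

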10.9. PREGNANCY TEST

Pregnancy test results will be provided in a listing only.

10.10. ECG

12-lead ECGs will be performed at Baseline and Weeks 3, 6, 12, 24 (or PW) of the Treatment Period, and Week 48 (or PW) of the Follow-Up Period. At infusion visits, ECGs will be performed prior to the infusion. The results will be recorded as normal or abnormal on the eCRF and all abnormal results will be evaluated as CS or NCS by the investigator.

Descriptive summaries of observed, change from Study Baseline, and change from HZN-001 Baseline values will be presented for each ECG parameter by visit, including RR, PR, QRS, QT, QTc, and QTcF and by treatment received in HZNP-TEP-301 and overall.

ECG shift tables will be presented providing the count of subjects with each type of finding (normal, abnormal - NCS, or abnormal - CS) at Study Baseline and HZN-001 Baseline compared to each post-baseline visit by treatment received in HZNP-TEP-301 with percentages based on subjects with a non-missing value at the Baseline and post-baseline visit.

Further, a summary will be provided of the count and percent of subjects with any post-Baseline assessment overall and by treatment received in HZN-TEP-301 in the following categories:

- QTcF >450 msec (males) or > 470 msec (females)
- QTcF >500 msec

Percentages will be based on the number of subjects with at least one post-Baseline value. Similar summaries will be provided by visit with the denominator based on the

number of subjects with data at the given visit overall and by treatment received in HZNP-TEP-301.

11. INTERIM ANALYSES

There are no planned interim analyses.

12. CHANGE FROM ANALYSIS PLANNED IN PROTOCOL

Protocol Version 3.0 (31-Jan-2019) specified that safety parameters would be summarized and presented in tables using the Safety Population. Instead, the ITT Population will be used for all summaries of efficacy and safety endpoints as it is expected that these populations will be identical. Also, PK Population was not referenced in the protocol. However, due to the addition of pharmacokinetic sampling and evaluation of pharmacokinetic parameters to the protocol, PK Population will be used for all PK analysis.

Protocol Version 3.0 (31-Jan-2019) referenced analyses relative to Study Baseline only. Analyses relative to HZN-001 Baseline will also be summarized.

Due to COVID-19 subject [REDACTED] delayed out of visit data will not be included in efficacy analyses. For further details refer to Appendix A.

14. PROGRAMMING CONSIDERATIONS

All tables, data listings, figures (TLFs), and statistical analyses will be generated using SAS® for Windows, Release 9.4 or higher (SAS® Institute Inc., Cary, NC, USA). Computer-generated table, listing and figure output will adhere to the following specifications.

14.1. GENERAL CONSIDERATIONS

- One SAS program can create several outputs.
- Each output will be stored in a separate file.
- Output files will be delivered in RTF format. Three PDF files will be provided for the final tables, listings, and figures separately.
- Numbering of TFLs will follow International Conference on Harmonization (ICH) E3 guidance

14.2. TABLE, LISTING, AND FIGURE FORMAT

14.2.1. General

- All TLFs will be produced in landscape format.
- All TLFs will be produced using the Courier New font, size 8
- The data displays for all TLFs will have a minimum 1-inch margin on all 4 sides.
- Headers and footers for figures will be in Courier New font, size 8.
- Legends will be used for all figures with more than 1 variable, group, or item displayed.
- TLFs will be in black and white (no color)
- Specialized text styles, such as bolding, italics, borders, and shading will not be used in the TLFs, unless otherwise specified. On some occasions, superscripts 1, 2, or 3 may be used.
- Only standard keyboard characters will be used in the TLFs. Special characters, such as non-printable control characters, printer-specific, or font-specific characters, will not be used. Hexadecimal-derived characters will be used, where possible, if they are appropriate to help display math symbols (e.g., μ). Certain subscripts and superscripts (e.g., m^2 , C_{trough}) will be employed on a case-by-case basis.
- Mixed case will be used for all titles, footnotes, column headers, and programmer-supplied formats, as appropriate.

14.2.2. Headers

- All output should have the following header at the top left of each page:
Horizon Pharma USA, Inc.

Protocol No: HZNP-TEP-302

- All output should have Page n of N at the top or bottom right corner of each page. TLFs should be internally paginated in relation to the total length (i.e., the page number should appear sequentially as page n of N, where N is the total number of pages in the table).
- The date output was generated should appear along with the program name as a footer on each page.

